The study population for this prospective randomized controlled trial will consist of male and female adult subjects over the age of 18 having surgery requiring NTI. Consent will be obtained by study personnel. Eligible patients will be screened by study personnel up to 1 week prior to scheduled surgery. Informed consent will be obtained in the preoperative holding area. This is a multicenter study. The MD Anderson Center is other site of the study. Each study site will enroll 56 subjects. A total of 112 subjects will be randomized to either the RRC group or control group. Oxymetazoline nasal spray will be administered with 1 spray per nostril preoperatively. Premedication with glycopyrrolate 0.2 mg and benzodiazepine at discretion of provider will be given preoperatively. Subjects will then be brought into the operating room and placed on all standard ASA monitors (BP cuff, EKG, pulse oximetry). One spray of oxymetazoline per nostril will again be administered. Standard preoxygenation will be used with a face mask and 100% O₂. After induction of anesthesia, provider will confirm mask ventilation and 1 more spray of oxymetazoline will be administered per nostril. Intubation will first be attempted via a naris (13). Size 6.5 nasotracheal RAE tubes (Shiley Nasal RAE Tracheal Tube with TaperGuard Cuff, manufactured by Covidien llc, Mansfield, MA 02048) will be used in female patients and size 7.5 in males (16). The tubes will be thermosoftened by allowing them to sit in warm saline prior to use (18). Water-based lubrication will be used for dilation and intubation. Time from insertion of RRC or NETT into nasal passage to first recording of end-tidal CO₂ will be recorded. Direct video laryngoscopy will be used to facilitate placement of the nasotracheal RAE tube. Five minutes after intubation, a non-collaborating anesthesia provider blinded to the method of intubation will grade the severity of bleeding by performing direct video laryngoscopy, inspecting the posterior pharynx and using a scale described originally by Sugiyama et al (19) and again by Earle et. al (20)- no epistaxis (no blood observed on either the surface of the tube or the posterior pharyngeal wall); mild epistaxis (blood apparent on the surface of the tube or posterior pharyngeal wall); moderate epistaxis (pooling of blood on the posterior pharyngeal wall); and severe epistaxis (a large amount of blood in the pharynx impeding nasotracheal intubation—before the epistaxis assessor enters the

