- Premature termination of procedure
- Unplanned hospital admission
- Unanticipated complications

4. Study Procedures:

- Identify and screen patients for study eligibility based on inclusion and exclusion criteria.
- Randomize subjects to the RRC or control group in a 1:1 ratio according to a computer-generated block randomization list (multi-center). (Research only)
- Administer premedication in the preoperative area (standard of care)
- Administer 1 spray of oxymetazoline per nostril in preoperative area (standard of care).
- Perform patency test in the preoperative area to determine which nares to use for initial attempt (standard of care).
- All standard monitoring (BP, EKG, and pulse oximeter) will be placed on all patients in the operating room (standard of care).
- Administer 1 spray of oxymetazoline per nostril prior to preoxygenation in the operating room (standard of care).
- Apply standard preoxygenation with full face mask (standard of care).
- Patients will undergo standardized NTI facilitated by RRC or direct insertion based on study group. Both procedures for nasal intubation are considered standard of care.
- Time from insertion of RRC or NETT into nasal passage to first recording of end-tidal CO₂ on monitor will be recorded (standard of care).
- Incidence and severity of epistaxis will be graded by a member of the anesthesia team according to a scale previously described and recorded (19, 20) (Research only).
- Anesthesia providers will record the number of intubation attempts, recruitment of the other naris, premature termination of the procedure, use of Magill forceps and use of rescue techniques to facilitate intubation, and other interventions, complications, or deviations from protocol during intubation in the EMR using a quick note.
- Postoperatively patients will be asked to rate their level of nasal pain on the side (left or right) that NTI was performed using a numerical rating scale at 30 and 60 minutes post emergence from anesthesia. Pain will be evaluated with Numeric Rating Scale (0=no pain and 10- worst pain imaginable). (Research only).

5. Sub-Study Procedures:

- N/A

6. Criteria for Inclusion of Subjects:

- Age > 18, male and female
- Subjects undergoing surgery requiring NTI
- ASA 1-3

7. Criteria for Exclusion of Subjects:

- History of anticoagulant use or coagulopathy
- History of latex allergy
- History of difficult airway
- Anticipated difficult airway requiring awake intubation

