Data and Safety monitoring plan includes the formation of a Data and Safety Monitoring Board (DSMB). As independent research expert, Board Certified Anesthesiologists [name] and [name] will review safety and data information. The DSMB will also obtain the results of the interim analysis after 50% enrollment.

12. Procedures to Maintain Confidentiality:

All participants will be given an identification number such that identifiable, personal information will not be used. There will be link to MR number. Subjects will be identified to collect data and verify the data. Every effort will be made to keep all data collection sheets confidential and any electronic data sets will be password protected and secure. Electronic documents will be de-identified according to information security policies. Paper documents will be shredded.

13. Potential Benefits:

There is no benefit to subjects. Use of the RRC may lead to a significant decrease in epistaxis and pain in patients undergoing NTI. Information gained from this study will potentially improve future outcomes in this patient population through reducing complications of nasotracheal intubation.

14. Data Sharing;

MD Anderson site will provide deidentified protocol requiring data via REDCap. UT Southwestern team who have access to MD Anderson Center RedCap will download the de-identified data. REDCap (<https://redcap.mdanderson.org>) is hosted on a secure server by MD Anderson Cancer Center's Department of Oncology Care & Research Information Systems. REDCap has undergone an annual Governance Risk & Compliance Assessment (since May 2014) by MD Anderson's Information Security Office and found to be compliant with HIPAA, Texas Administrative Codes 202-203, University of Texas Policy 165, federal regulations outlined in 21CFR Part 11, and UTMDACC Institutional Policy #ADM0335.

Those having access to the data include the study PI's and research team personnel of both study sites. Users are authenticated against MDACC's Active Directory system. External collaborators are given access to the database once approved by the PI, with their access expiring in 6 months, but renewable in 6 months increments at the request of the PI. The application is accessed through Secure Socket Layer (SSL).

15. Biostatistics: (omit this section for peer-reviewed research such as cooperative group, or NIH- sponsored studies, and for industry-sponsored research which has been submitted to FDA)

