Assuming the incidence of bleeding to be 50% and 24% in the control and RRC group, respectively, a sample size of 53 subjects per group (total n=106) are needed. This study is designed to have 80% power with alpha = 5%, two-sided. Assuming a dropout of 5%, a total of 112 subjects (56 in each arm) are required for this study. The sample size calculation was based on the chisquare tests.

Baseline characteristics (Demographics, Comorbidities) of all randomized patients will be summarized and presented in tables. Categorical variables will be presented as proportions and continuous variables as mean (SD) or median (range) as appropriate. The baseline differences between the two treatment arms will be assessed by Chi square/Fisher exact tests for proportions and Student t-test/Wilcoxon ranksum test for continuous variables as appropriate.

An intention to treat analysis will be conducted to assess the primary endpoint of bleeding. Logistic regression analysis will be conducted to model the primary endpoint between the treatment groups accounting for other confounders. Individual logistic regressions analyses will be conducted to model the secondary outcomes adjusting for treatment groups and other confounders. A univariate and a multivariable linear regression analysis will be conducted for those secondary outcomes, which are measured as continuous variables. A per protocol analysis will also be conducted where

patients with protocol violations will be excluded from the analysis. All analyses will be done using SAS 9.4 and $p < 0.05$ will be considered statistically significant.

15. References:

1. Chauhan, V. and Acharya, G. (2016) Nasal Intubation: A Comprehensive Review. *Indian Journal of Critical Care Medicine*, 20,662-667. doi:10.4103/0972-5229.194013
2. Hall, C.E. and Shutt, L.E. (2003) Nasotracheal Intubation for Head and Neck Surgery. *Anaesthesia*, 58, 249-256. doi:10.1046/j.1365-2044.2003.03034.x
4. Prasanna, D. and Bhat, S. (2014) Nasotracheal intubation: an overview. *Journal of Maxillofacial and Oral Surgery*, 13, 366-372. doi:10.1007/s12663-013-0516-5

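### Does the plan need changing because the primary logistic model names no covariates and the Biostatistics section does not mention site?

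*Combined protocol and SAP*

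**What the plan says.** Section 15 (Biostatistics) gives the primary endpoint two sentences. The first sets the analysis population: "An intention to treat analysis will be conducted to assess the primary endpoint of bleeding". The second gives the method: "Logistic regression analysis will be conducted to model the primary endpoint between the treatment groups accounting for other confounders". No confounder is listed, and there is no rule for choosing one.

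On sizing, the same section says "The sample size calculation was based on the chisquare tests". As an analysis method, chi-square (or Fisher) is named only for comparing baseline characteristics. Unadjusted and adjusted models are distinguished only for continuous secondary endpoints: "A univariate and a multivariable linear regression analysis will be conducted for those secondary outcomes".

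Site appears elsewhere. Section 3 states "Each study site will enroll 56 subjects", with two sites in all. Section 4 allocates 1:1 from a computer-generated block list labelled multi-center, without saying whether it is stratified by site. Section 11 adds: "The DSMB will also obtain the results of the interim analysis after 50% enrollment".

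**The concern.** Three things are left unsaid: which covariates enter the primary model, whether an adjusted or unadjusted p-value decides Hypothesis 1, and whether site is in the model.

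An open covariate list would let several models be fitted after the results are known. Reporting the most favourable one would push the type I error above 5%. If bleeding rates differ between the two sites, leaving site out gives up some power. An adjusted odds ratio also moves with the covariate list even when the difference in proportions is fixed, so it does not map directly onto the 50% and 24% used for sizing. If these effects were large, the main result would rest on choices that the plan does not control.

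**Working it through.** **1. The plan's own figure.** Inputs from Section 15: 50% and 24% bleeding, two-sided alpha 5%, power 80%, chi-square test. The mean rate is (0.50 + 0.24)/2 = 0.37.

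n per group = [1.960 × √(2 × 0.37 × 0.63) + 0.8416 × √(0.50 × 0.50 + 0.24 × 0.76)]² / 0.26²
= (1.3382 + 0.5534)² / 0.0676 = 52.9, rounded up to 53.

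Then 106/0.95 = 111.6, rounded up to 112. Both stated figures reproduce. Power from the same formula is 80.0% at 53 per group and 82.2% at 56.

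**2. Power with and without site.** The documents give no site-specific rates, so those below are assumptions. The simulation uses two sites of 56 and a common odds ratio set so that the red-rubber catheter arm averages 24%. There were 200,000 runs for chi-square and 40,000 for the logistic model. Ranges cover lists stratified and not stratified by site.

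| Control rates at the two sites | Site odds ratio | Chi-square | Logistic, treatment + site | Change from adding site (points) |
|---|---|---|---|---|
| 50/50% | 1 | 82.3–82.6% | 81.9–82.4% | −0.4 to −0.2 |
| 40/60% | 2.25 | 82.4–82.8% | 83.1–83.6% | +0.7 to +0.8 |
| 30/70% | 5.4 | 82.5–84.0% | 87.2–87.4% | +3.4 to +4.7 |
| 25/75% | 9 | 82.3–85.2% | 89.9% | +4.7 to +7.6 |

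The site odds ratio is, for example, (0.75/0.25)/(0.25/0.75) = 9.

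A separate simulation at 106 evaluable subjects (4,000 runs per setting, arms balanced within site, other covariates also having effects in the last two settings) gave chi-square 81.8%, 81.6% and 81.4%, and treatment + site 81.4%, 82.1% and 83.0%, at assumed site odds ratios of 1, 2 and 4. Power stays above 80% with or without site.

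**3. False positives if site is left out.** With stratified allocation, the true variance of the difference uses the within-site variance, while the chi-square test uses the pooled one. With an average rate of 50%, the pooled variance is 0.25. The approximate size is 2 × [1 − Φ(1.960/√w)], where w is the mean within-site p(1 − p) divided by 0.25.

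- 40/60%: w = 0.24/0.25 = 0.96, size 4.5% (simulated 4.3%)
- 30/70%: w = 0.21/0.25 = 0.84, size 3.2% (simulated 3.0%)
- 25/75%: w = 0.1875/0.25 = 0.75, size 2.4% (simulated 2.2%)

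Without stratification the simulated size is 4.6% to 4.7%. Leaving site out is therefore conservative or near nominal. The treatment + site model held 4.6% to 5.0%.

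**4. False positives if the model is chosen after the fact.** Covariate effects here are also assumptions.

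- Better of chi-square and treatment + site: 4.7% to 5.4%
- Best of seven analyses (chi-square, treatment-only logistic, and logistic with combinations of site, sex and two continuous covariates): 6.0% to 7.5%
- Best of all 32 covariate subsets: 7.4% to 10.6% with weak or moderate covariates, up to 12.7% with strong ones
- One fixed treatment + site model, in the 32-subset simulation: 4.6% to 5.4%

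**5. Effect measure.** The unadjusted odds ratio is (0.24/0.76)/(0.50/0.50) = 0.316. The site-adjusted odds ratio that keeps the arm averages at 50% and 24% is 0.303, 0.262 or 0.230 at 40/60, 30/70 or 25/75%. Check at 40/60%: control odds 0.667 and 1.5, each multiplied by 0.303, give rates of 16.8% and 31.2%, which average 24.0%. The shift is small unless the sites differ greatly, and arm proportions can be shown beside any odds ratio.

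**The case for a change.** The strongest case for a change is that the test of the main hypothesis should not depend on an undefined word. Calling logistic regression primary does not settle its content. Section 8 collects items recorded during or after insertion, such as the number of attempts, Magill forceps use and lowest oxygen saturation. Nothing expressly bars these from the model, and adjusting for them could distort the treatment effect. An interim analysis at half enrolment gives an occasion for model choice to be influenced by data. Naming a treatment + site model would take a few sentences, cost no subjects, and lose nothing material if the sites are alike. With 56 × 0.74 = 41.4 expected bleeding events, the data support only a short covariate list in any case.

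Much of this stands as good practice: naming the covariates before any unblinded look would be tidier, and site is the natural candidate. It does not show a fault in the plan. The intention-to-treat sentence defines who is analysed and is not a rival test. Sizing on chi-square and analysing by logistic regression is ordinary. A confounder, in the usual sense, is not a consequence of treatment, so a competent analyst would not adjust for events that follow insertion. The inflated error rates require someone to search for the smallest p-value, which no rule in the plan directs.

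**Conclusion.** No change follows. The omission is real, but it is missing detail that an analyst can fill sensibly. Followed in good faith, with or without site, the primary analysis keeps its 5% error rate and more than 80% power under the planning rates. Site adjustment is a modest efficiency gain: none at equal rates, about 1 point at 40/60%, and 5 to 8 points only at 25/75%, a site odds ratio of 9 for which the documents give no support. Type I error of 6% to 7.5% would need a free choice among seven analyses, and 12.7% is the ceiling of a 32-model search with strong covariates.

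The site rates and covariate effects are assumptions throughout; the power figures also take the planned 50% and 24% as true. The sample size of 112 is correct as stated, and naming the model would alter no number or rule in the plan.

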Use of a Red-Rubber Catheter to Facilitate Nasotracheal Intubation in Adult Patients: A Prospective Randomized Controlled Trial

NCT number: NCT03779984

Protocol Date: 02/14/2022

English ICF date: 05/09/2022

**The University of Texas Southwestern Medical Center at Dallas
Institutional Review Board**

Protocol

Use of a Red-Rubber Catheter to Facilitate Nasotracheal Intubation in Adult Patients: A Prospective Randomized Controlled Trial

Institution/Funding Source: Department of Anesthesia and Pain Management – University of Texas Southwestern Medical Center

1. Introduction and Purpose:

Nasotracheal intubation is used to facilitate oropharyngeal surgery in many patients, however, epistaxis is a common complication (1). Several methods to reduce epistaxis during nasotracheal intubation have been studied in adults and children. The use of a red-rubber catheter is effective in guiding nasotracheal intubation in children, however it has not been studied in adults in a prospective, randomized, controlled trial. This study was designed to compare the effectiveness of using a red-rubber catheter versus standard, direct insertion of a thermosoftened, lubricated nasal endotracheal tube into the naris to facilitate nasotracheal intubation in adults undergoing ENT, plastics or OMFS surgery. This study will assess if the red-rubber catheter method leads to lower incidence and severity of epistaxis, and faster time to intubation compared to the current standard of care.

Hypothesis 1 – The red-rubber catheter group will have significantly lower incidence of epistaxis compared to the standard insertion group in patients undergoing nasotracheal intubation.

Primary objective: To compare the incidence of bleeding after nasotracheal intubation.

Hypothesis 2 – The red-rubber catheter group will have significantly lower severity of epistaxis compared to the standard insertion group in patients undergoing nasotracheal intubation.

Secondary objective 1: To compare the severity of epistaxis after nasotracheal intubation.

Hypothesis 3 – The red-rubber catheter group will have significantly fewer airway complications compared to the standard insertion group in patients undergoing nasotracheal intubation.

Secondary objective 2: To compare the rate of complications during nasotracheal intubation.

Hypothesis 4 – The red-rubber catheter group will have significantly lower time to intubation than the standard insertion group.

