operating room, requiring suction for intubation or necessitating urgent orotracheal intubation.) Degree of nasal pain on the side of intubation will be rated on a numerical rating scale at 30 and 60 minutes in the post-anesthesia care unit (9).

The removal/reinsertion of the laryngoscope and endotracheal tube or switching of the laryngoscopist will be evaluated as a new intubation attempt.

The study duration starts from operating room preoperative holding area admission to discharge from the Post Anesthesia Care Unit (PACU).

RRC group: The funnel end of a RRC (Bard All-Purpose Urethral Catheter, manufactured by C. R. Bard, Inc, Covington, GA 30014 USA) will be securely attached to a room-temperature nasotracheal tube. A 20 Fr RRC will be used with the size 7.5 nasotracheal RAE tube and an 18 Fr RRC will be used with the size 6.5 nasotracheal RAE tube. The tubes will be warmed in saline prior to use (18). Water-based lubrication will be applied to the RRC. The rounded end of the catheter will be introduced into a naris and advanced to the posterior oropharynx and visualized with a laryngoscope. The catheter will then be removed from the end of the nasotracheal tube and withdrawn through the mouth. The nasotracheal tube will then be guided into the trachea past the vocal cords under direct visualization with CMAC video laryngoscope MAC 3 or 4 blade with or without the assistance of Magill forceps as determined by the provider (17).

Control group: The NETT will be warmed in saline prior to use (18). Water-based lubrication will be applied on the nasotracheal RAE tube. The nasotracheal tube will be inserted into the nasal passage and advanced into the oropharynx. The nasotracheal tube will then be guided into the trachea past the vocal cords under direct visualization with CMAC video laryngoscope MAC 3 or 4 blade with or without the assistance of Magill forceps as determined by the provider.

Outcome Measures:

- Incidence of bleeding in posterior oropharynx
- Severity of bleeding in posterior oropharynx
- Need to suction the posterior oropharynx to facilitate intubation
- Time from first insertion of catheter or nasal RAE tube to ETCO₂
- Number of intubation attempts
- Recruitment of the other naris for intubation
- Use of Magill forceps to facilitate intubation
- Use of rescue technique (fiberoptic, oral intubation) to facilitate intubation
- Patient rating of nasal pain on side of intubation
- Anesthesiologist intervention outside of protocol

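### Binary secondary outcomes, including those behind Hypothesis 3, are analysed by ordinary logistic regression with no method for an arm without events

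*Combined protocol and SAP*

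**What the plan says.** Hypothesis 3 in section 1 is a single claim: "The red-rubber catheter group will have significantly fewer airway complications compared to the standard insertion group". The objective attached to it is "To compare the rate of complications during nasotracheal intubation". Neither lists the events that count or says whether they are combined.

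The Outcome Measures list in section 3 supplies candidates, among them "Use of rescue technique (fiberoptic, oral intubation) to facilitate intubation" and "Premature termination of procedure", with no expected rate for any of them. Magill forceps use is on the same list, although the intubation procedure allows it in both arms, "with or without the assistance of Magill forceps as determined by the provider". Suction is listed too, and both suction and urgent oral intubation are also criteria for the severe grade of epistaxis.

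Section 15 (Biostatistics) gives the analysis: "Individual logistic regressions analyses will be conducted to model the secondary outcomes adjusting for treatment groups and other confounders". The confounders are not named, the software is SAS 9.4, and the significance level is 0.05. The section's only mention of an exact test concerns baseline tables: "The baseline differences between the two treatment arms will be assessed by Chi square/Fisher exact tests for proportions".

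**The concern.** Ordinary logistic regression breaks down when one arm has no events. The log odds ratio runs off to infinity and its standard error grows faster still. The Wald p-value then reflects where the iterations stopped, not the data. The RRC arm is the one expected to do better, so the result most favourable to the trial's hypothesis (no events on RRC) could be reported as non-estimable or non-significant. Adjusting for several confounders thins the data further.

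A second gap compounds this. With no stated Hypothesis 3 endpoint, the reader cannot tell which regression answers it, and the choice could be made after the results are known.

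**Working it through.** **The plan's own figure.** Section 15 assumes bleeding in 50% v 24%, 80% power and two-sided 5%. With pooled variance and no continuity correction, n = [1.96·√A + 0.842·√B]² / 0.26² = 52.9, so 53 per arm. Here A is twice the product of 0.37 and 0.63, and B is the product of 0.50 and 0.50 plus the product of 0.24 and 0.76. Dividing 53 by 0.95 gives 55.8, so 56 per arm and 112 in total. Both stated figures reproduce. They concern bleeding only, and no figure is given for complications.

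**Chance of no RRC events.** This is (1 − p)^53:
- p = 1%: 0.99^53 = 59%
- p = 2%: 0.98^53 = 34%
- p = 5%: 0.95^53 = 7%

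With 56 per arm, the first two become 57% and 32%.

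**Why the Wald test fails.** Let a be control events, b RRC events and n = 53. The unadjusted log odds ratio is ln[b(n − a)/(a(n − b))], with SE = √(1/a + 1/b + 1/(n − a) + 1/(n − b)). As b goes to 0 the numerator grows like ln b and the SE like 1/√b, so the ratio goes to 0. Fitting the model numerically at 0 RRC events and 1 to 12 control events gave Wald p-values of about 0.56 to 0.98, depending on when the iterations stopped. None was significant.

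At b = 1 and a = 8 the test works again: the odds are 1/52 on RRC and 8/45 in control, so the odds ratio is 0.108, the log is −2.22, the SE is 1.08, z = −2.06 and p = 0.04.

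**Fewest control events for p < 0.05, 53 per arm:**

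| RRC events | Wald | Fisher | Firth | Score (chi-square) | Likelihood ratio |
|---|---|---|---|---|---|
| 0 | never | 6 | 5 | 4 | 3 |
| 1 | 8 | 8 | 7 | 7 | 6 |
| 2 | 9 | 10 | 9 | 8 | 8 |
| 3 | 10 | 11 | 10 | 10 | 10 |

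**Power.** Full enumeration of two binomials, 53 per arm, unadjusted, with a zero-cell Wald test counted as non-significant. All rates are assumed.

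| Control v RRC | Either arm empty | Wald | Fisher | Firth | Score (chi-square) | Likelihood ratio |
|---|---|---|---|---|---|---|
| 12% v 2% | 34% | 15% | 35% | 48% | 54% | 63% |
| 10% v 2% | 35% | 8% | 22% | 33% | 41% | 51% |
| 8% v 3% | 21% | 3% | 7% | 13% | 18% | 26% |

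**False-positive rate.** With a true 5% in both arms, the likelihood-ratio test rejects 8.6% of the time, score 4.4%, Firth 2.3% and Fisher 0.8%. Part of the likelihood-ratio test's apparent power is therefore an inflated error rate.

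**Estimate.** At 6 control v 0 RRC events the ordinary odds ratio is 0, with an infinite log. In an unadjusted two-by-two table Firth's estimate adds 0.5 to each cell. The odds become 0.5/53.5 on RRC and 6.5/47.5 in control, a ratio of 0.07, which is finite and comes with a profile-likelihood interval.

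**The case against.** The strongest reply is that the plan never says Wald. Likelihood-ratio and score tests from the same model still detect a difference with an empty RRC arm, from 3 and 4 control events respectively. A reader might infer that the plan as written must give a non-significant answer when RRC has no complications. The documents do not support that: it follows only under Wald inference, and the plan leaves the test open. What stands is that nothing in the plan rules Wald out. The other two tests also leave the odds ratio non-estimable, and the likelihood-ratio test exceeds its nominal error rate at 5% v 5%.

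A reader might also infer that few RRC events are as damaging as none. They are not. At one RRC event Wald needs the same 8 control events as Fisher, and from two onward it needs no more than Fisher.

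Nor does the text commit to one regression for every listed item. One regression per secondary objective is an equally fair reading. The fault is that the endpoint is undefined, not that a component-by-component plan has been stated.

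It is tempting, too, to calculate the power of a composite by treating its components as independent. Section 3 counts removal and reinsertion of the laryngoscope and tube as a new attempt, so a change of naris or oral rescue will usually also count as a repeat attempt. The components overlap and independence is implausible.

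Finally, rarity is assumed. Excluding known difficult airways makes low rates of rescue plausible, but the documents give no rates, and Magill use or suction need not be rare.

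**Conclusion.** The concern holds in a limited form. The plan uses ordinary logistic regression for binary secondary outcomes and has no rule for sparse data. When an arm is empty, the odds ratio is non-estimable and a Wald test cannot be significant. At assumed rates of 12% v 2%, that puts power at about 15% for Wald against 48% for Firth. The failure is essentially confined to zero events. Its likelihood depends on rates the documents do not give, and the calculations are unadjusted because the confounders are unnamed.

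Changing the method does not make Hypothesis 3 well powered: at 8% v 3% Firth reaches only 13%. That the Hypothesis 3 endpoint is undefined needs no assumed rate. The primary endpoint is not affected by either gap.

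**What to change.** In section 15, replace ordinary logistic regression for sparse binary secondary outcomes with Firth-penalised logistic regression. Report profile-likelihood intervals and penalised likelihood-ratio p-values, and adjust for few or no covariates. An exact test with a risk-difference interval is an acceptable alternative. Name the chosen test and the rule for when an outcome counts as sparse.

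Before unblinding, the investigators should state which items already collected form the single Hypothesis 3 endpoint, and report the other items descriptively. Which items count is a clinical judgement. Suction and urgent oral intubation both overlap with the severe epistaxis grade, so whatever rule is applied to one should be applied to the other.

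This needs SAP wording and slightly more analysis work, with no new data. The drawback is that Firth estimates are shrunk toward no effect, which the report should say.

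### Section 15 (Biostatistics) has no sparse-event method for the binary secondary outcomes: if the Wald test of ordinary logistic regression is used and one arm has no events, p is near 1 whatever the other arm shows

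*Combined protocol and SAP*

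**What the plan says.** Hypothesis 3 in Section 1 (Introduction and Purpose) is directional: "The red-rubber catheter group will have significantly fewer airway complications compared to the standard insertion group". Secondary objective 2, which goes with it, compares complication rates but does not say which events count.

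The Outcome Measures list in Section 3 includes discrete events such as "Use of rescue technique (fiberoptic, oral intubation) to facilitate intubation" and "Premature termination of procedure", as well as unplanned admission. No expected frequency is given for any of them.

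Section 15 (Biostatistics) gives one method for secondary outcomes that are not continuous: "Individual logistic regressions analyses will be conducted to model the secondary outcomes adjusting for treatment groups and other confounders". Continuous secondary outcomes go to linear regression. The software is SAS 9.4 and the threshold is p < 0.05. The section does not say whether the p-value is Wald, score or likelihood-ratio, does not name the confounders, and says nothing about an arm with no events. Fisher's exact test appears only for baseline comparisons.

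**The concern.** Section 7 excludes patients with a history of difficult airway, abnormal nasal anatomy or coagulopathy, so some of the listed events may be uncommon. With 56 patients per arm, an arm with no events is then a realistic result. An event-free catheter arm is also the result most favourable to Hypothesis 3.

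If every patient in one arm is event-free, the treatment coefficient has no finite maximum-likelihood estimate. The fitted log odds ratio drifts to a large value and its standard error grows far faster, so the Wald ratio goes to about 0. Adding covariates does not cure this, because the arm indicator still predicts the absence of events perfectly in that arm. A real difference in complications could then be reported as non-significant because of the test used. If the method is chosen only after the failure is seen, the choice depends on the data.

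**Working it through.** **The plan's own figure.** The inputs are in Section 15: "Assuming the incidence of bleeding to be 50% and 24% in the control and RRC group, respectively", 80% power, two-sided 5%, and "The sample size calculation was based on the chisquare tests". With pooled proportion (0.50 + 0.24)/2 = 0.37:

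n = [1.960·√(2·0.37·0.63) + 0.842·√(0.50·0.50 + 0.24·0.76)]² / 0.26² = (1.338 + 0.553)² / 0.0676 ≈ 52.9, so 53 per arm.

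For dropout, 106/0.95 = 111.6, so 112. This agrees with "Assuming a dropout of 5%, a total of 112 subjects (56 in each arm) are required for this study". The sample size reproduces and is not in dispute. It was set for bleeding, not for complications.

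**One table by each test.** Take 0/56 (catheter) v 8/56 (control), unadjusted:

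- Wald: the iterations stop at log OR −18.41 with SE 3258. z = −18.41/3258 = −0.006, p = 0.996.
- Fisher: 2 × (56·55·…·49)/(112·111·…·105) = 2 × 0.00299, p = 0.006.
- Likelihood ratio: 2[8 ln 2 + 48 ln(48/56) − 104 ln(104/112)] = 11.71, p = 0.0006.
- Score (Pearson chi-square): (8/56)² / [2·(8/112)(104/112)/56] = 8.62, p = 0.003.
- Firth: in a 2×2 table the penalty adds 0.5 to each cell. The fitted rates are 8.5/57 and 0.5/57, and under the null 9/114. Twice the penalised log-likelihood difference is 2(−26.87 + 31.49) ≈ 9.23, p = 0.002.

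The Wald p-value stays between 0.993 and 0.996 for every control count tried from 3 to 12 against zero. Fisher's p is below 0.05 from 6 control events upward (0 v 6: 0.027). With one event in the sparse arm the failure disappears: at 1 v 8, Wald is 0.040 and Fisher 0.032.

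**How often an arm is empty.** The chance that the catheter arm has no events is (1 − p)⁵⁶: 0.99⁵⁶ = 57%, 0.98⁵⁶ = 32%, 0.95⁵⁶ = 6%.

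**Rejection rates.** Let k be control events and m catheter events. For each test, sum Bin(k; 56, p_C) × Bin(m; 56, p_R) over all tables with p < 0.05. All rates are assumed. A zero cell counts as non-rejection for Wald.

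| True rates, control v catheter | Wald | Fisher | Firth |
|---|---|---|---|
| 12% v 1% | 14% | 51% | 65% |
| 15% v 2% | 34% | 59% | 70% |
| 15% v 5% | 29% | 29% | 39% |
| 5% v 1% | 0.2% | 3.6% | 9% |
| 5% v 0% | 0% | 6% | 15% |

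Under equal rates (nominal 5%):

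| Common rate | Wald | Likelihood ratio | Score | Fisher | Firth |
|---|---|---|---|---|---|
| 3% | 0.0% | 9.0% | 3.3% | 0.3% | 1.0% |
| 5% | 0.3% | 8.4% | 4.5% | 0.9% | 2.5% |

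These enumerations are unadjusted. The plan names no confounders, so the adjusted analysis cannot be enumerated.

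**The case against.** **The plan never says Wald.** This stands. A reader might infer that logistic regression is bound to miss a catheter effect that removes a complication. The text does not support that, because it leaves the test open. The score test of the same unadjusted model gives p = 0.003 at 0 v 8, holds its size in the table above, and has power of 72% at 12% v 1% and 75% at 15% v 2%, more than Firth. The fault is therefore an unspecified test with no sparse-data rule, not logistic regression as such. The score test does leave the odds ratio infinite, and its behaviour was checked only without covariates.

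**Sparsity is assumed.** This also stands. The documents give no rate and define no complication endpoint. A composite that took in Magill forceps use, suctioning or repeat attempts might be common enough to avoid empty cells. A reader might also count severe epistaxis among the rare complications, but in Section 3 it is the top level of the severity scale that serves Hypothesis 2.

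**The loss depends on the scenario.** It is large only when the control rate is moderate and the catheter rate is close to zero. At 15% v 5%, Wald and Fisher are level (29.0% v 29.3%). At 20% v 10%, Wald is ahead of Fisher (28.2% v 22.5%). At control rates near 5% there is little power to lose. No single loss figure can be attached to this trial.

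**An infinite odds ratio is easy to see, and an analyst would react.** That is likely, but the reaction would be chosen after seeing the data. One easy alternative, the ordinary likelihood-ratio p-value, rejects too often when events are rare.

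**Conclusion.** The concern holds as a gap in the specification of the binary secondary outcomes. Section 15 prescribes ordinary adjusted logistic regression, names no test, and has no rule for an arm with zero or few events. If the Wald p-value is used, a zero cell gives p near 1 regardless of the other arm. That result needs no assumption about rates.

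The cost in power does need one. At 56 per arm, Firth gains over Wald by 51 points at 12% v 1% (65 − 14), 36 points at 15% v 2% (70 − 34) and 10 points at 15% v 5% (39 − 29). Its size stays below 5% at both null rates in the table. The gain is of little use where control rates are about 5% or lower.

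The primary endpoint, planned at 50% v 24%, is not sparse and is unaffected. This is an inexpensive improvement to secondary analyses for which the trial was not sized, and it does not threaten the main result.

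**What to change.** In Section 15 (Biostatistics), state that the binary secondary outcomes will be analysed by Firth penalised logistic regression (PROC LOGISTIC with the FIRTH option), with p-values and confidence intervals from the profile penalised likelihood. State also that the model will contain treatment arm only when an outcome has fewer than about 10 events in total.

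An exact confidence interval for the risk difference may be reported alongside. Fisher's test should not replace Firth as the main p-value, because it is itself conservative (size 0.3% at 3% v 3% and 0.9% at 5% v 5%).

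The cost is one sentence in the plan and one option in the SAS code, with no extra patients or data. The small downside is that very sparse outcomes will not be covariate-adjusted.
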